### Margin of Safety for Oral Administration of LY3475070 Based on Administered Dose and Predicted Exposure

	Dose (mg/kg)	Dose (mg/m  )	Dose Multiple a to Starting Dose (to maximum dose)	AUC (ng*h/mL)	Exposure Multiple b to Starting Dose (to maximum dose)
Human (150 mg) c	CCI	CCI	–	CCI	–
Human (1000 mg) d	CCI	CCI	–	CCI	–
Rat NOAEL e			32x (4.9x)		43x (6.5x)
Dog NOAEL f			22x (3.2x)		14x (2.2x)

Abbreviations: AUC = area under the curve; IVIVE = in vitro to in vivo extrapolation; NOAEL = no-observed-adverse-effect level.

- a Dose multiple is the dose in animals/dose in humans based on mg/m^2. Doses were converted from mg/kg to mg/m^2 using a km conversion factor of 6 for the rat, 20 for the dog, and 37 for a 60-kg human.
- b Exposure multiple is the calculated AUC in animals/predicted AUC in humans.
- c Clinical starting dose (150 mg). Exposure is predicted AUC using IVIVE of hepatocyte clearance.
- d Maximum planned clinical dose (1000 mg). Exposure is predicted AUC using IVIVE of hepatocyte clearance.
- e NOAEL in a rat 1-month repeat dose toxicity study (Study 8401913). Average of male and female rat AUC on Day 28.
- f NOAEL in a dog 1-month repeat dose toxicity study (Study 8401914). Average of male and female dog AUC on Day 28.

#### 4.3.2. Pembrolizumab

The planned dose of pembrolizumab for this study is 200 mg Q3W. Based on the totality of data generated in the Keytruda development program, 200 mg Q3W is the appropriate dose of pembrolizumab for adults across all indications and regardless of tumor type. As outlined below, this dose is justified by:

- Clinical data from 8 randomized studies demonstrating flat dose- and exposure-efficacy relationships from 2 mg/kg Q3W to 10 mg/kg every 2 weeks (Q2W),
- Clinical data showing meaningful improvement in benefit-risk including overall survival at 200 mg Q3W across multiple indications, and
- Pharmacology data showing full target saturation in both systemic circulation (inferred from PK data) and tumor (inferred from physiologically-based PK [PBPK] analysis) at 200 mg Q3W.

Among the 8 randomized dose-comparison studies, a total of 2262 participants were enrolled with melanoma and non-small cell lung cancer (NSCLC), covering different disease settings (treatment naïve, previously treated, PD-L1 enriched, and all-comers) and different treatment settings (monotherapy and in combination with chemotherapy). Five studies compared 2 mg/kg Q3W versus 10 mg/kg Q2W (KN001 Cohort B2, KN001 Cohort D, KN002, KN010, and KN021), and 3 studies compared 10 mg/kg Q3W versus 10 mg/kg Q2W (KN001 Cohort B3, KN001 Cohort F2 and KN006). All of these studies demonstrated flat dose- and exposure-response relationships across the doses studied representing an approximate 5- to 7.5-fold difference in exposure. The 2 mg/kg (or 200 mg fixed-dose) Q3W provided similar responses to the highest doses studied. Subsequently, flat dose-exposure-response relationships were also observed in other tumor types including head and neck cancer, bladder cancer, gastric cancer and classical Hodgkin Lymphoma, confirming 200 mg Q3W as the appropriate dose independent of the tumor type. These findings are consistent with the mechanism of action of pembrolizumab, which acts by interaction with immune cells, and not via direct binding to cancer cells.

Additionally, pharmacology data clearly show target saturation at 200 mg Q3W. First, PK data in KN001 evaluating target-mediated drug disposition (TMDD) conclusively demonstrated saturation of PD-1 in systemic circulation at doses much lower than 200 mg Q3W. Second, a PBPK analysis was conducted to predict tumor PD-1 saturation over a wide range of tumor penetration and PD-1 expression. This evaluation concluded that pembrolizumab at 200 mg Q3W achieves full PD-1 saturation in both blood and tumor.

Finally, population PK analysis of pembrolizumab, which characterized the influence of body weight and other participant covariates on exposure, has shown that the fixed-dosing provides similar control of PK variability as weight based dosing, with considerable overlap in the distribution of exposures from the 200 mg Q3W fixed dose and 2 mg/kg Q3W dose. Supported by these PK characteristics, and given that fixed-dose has advantages of reduced dosing complexity and reduced potential of dosing errors, the 200 mg Q3W fixed-dose was selected for evaluation across all pembrolizumab protocols.

#### **4.4. End of Study Definition**

The end of the study is defined as the date of the last visit of the last participant in the study or last scheduled procedure shown in the SoA (Section 1.3) for the last participant in the study globally.

## 5. Study Population

Prospective approval of protocol deviations to recruitment and enrollment criteria, also known as protocol waivers or exemptions, is not permitted.

### 5.1. Inclusion Criteria

#### Type of Participant and Disease Characteristics for Phase 1a

Participants are eligible to be included in the study only if the following **cohort-specific** criteria apply:

1. Patients must be, in the judgement of the investigator, an appropriate candidate for experimental therapy and must have progressed through or be intolerant to therapies known to confer clinical benefit.
2. Patients must have archived tumor tissue available for biomarker analysis or be able and willing to undergo a baseline biopsy. On-treatment biopsy is optional (See Section 8.8).
3. Male or female participant with histological or cytological evidence of 1 of the following cancers that is metastatic, unresectable locally advanced, or locally recurrent:
  - a. Triple negative breast cancer. Triple-negative receptor status is defined as  $\leq 10\%$  for estrogen and progesterone receptor expression, and human epidermal growth factor receptor 2 (HER2) negative per ASCO/CAP HER2 testing guideline.
    - i. Patient must have received treatment for metastatic disease
    - ii. Prior PD-1/L1 inhibitor is allowed;
  - b. Pancreatic cancer
    - i. Must have received chemotherapy for advanced or metastatic disease (e.g. gemcitabine containing regimen or modified FOLFIRINOX);
    - ii. Patients with known microsatellite instability-high (MSI-H) tumor should have received prior PD-1/L1 inhibitor therapy;
  - c. Non-small cell lung cancer
    - i. Patient must have experienced progressive disease on or within 3 months of completing prior PD-1/L1 based inhibitor therapy (i.e., have refractory disease).
    - ii. Patients must have received treatment for metastatic disease. Patients with targetable mutations (e.g., ROS1, ALK, BRAF, and EGFR) must have received approved mutation-targeted therapy;
    - iii. Patients with targetable mutations are not required to have received PD-1/L1 inhibitors
  - d. Renal cell carcinoma, clear cell predominant subtype
    - i. Patient must have experienced progressive disease on or within 3 months of completing prior PD-1/L1-based inhibitor therapy (i.e., have refractory disease).
  - e. Cutaneous melanoma (CM)
    - i. Patient must have experienced progressive disease on or within 3 months of completing prior-PD-1/L-based inhibitor therapy (i.e., have refractory disease).
  - f. Castrate resistant prostate cancer

- i. Patient must have received treatment for metastatic disease; which should have included at least 1 next generation hormonal agent (e.g., Abiraterone, enzalutamide)
  - ii. Patients with small-cell or neuro-endocrine histologies will be excluded
- g. Epithelial ovarian cancer
  - i. Patient must have received treatment for metastatic disease, including a platinum-based therapy. Patients in first relapse after adjuvant platinum therapy whose disease is platinum-sensitive should have received treatment with platinum-based therapy for recurrent disease.

### **Type of Participant and Disease Characteristics for Phase 1b**

- 4. Patients must be, in the judgement of the investigator, an appropriate candidate for experimental therapy and must have either refused, progressed through or be intolerant to therapies known to confer clinical benefit.
- 5. Patients must have metastatic, unresectable locally advanced, or locally recurrent disease.
- 6. Patients must be able and willing to provide the protocol required biopsies at baseline and during study treatment period (See Section 8.8). For patients enrolled in Cohorts D1 and D2, biopsies are only required if patient has accessible soft tissue metastasis.
- 7. Cohorts C1 and C2: Patients positive for CD73 expression (CD73 expression determined by central IHC testing of pretreatment tumor biopsy; cut-off will be determined by the Sponsor)
  - a) Patients must have NSCLC, RCC or melanoma;
  - b) Patients must be refractory to prior PD-1/L1 inhibitor defined as: patients must have had prior PD-1/L1 therapy within 12 weeks of starting dosing on this study. Patients must have progressed on treatment with an anti-PD-1/L1 mAb administered either as monotherapy, or in combination with other checkpoint inhibitors or other therapies, with no intervening therapy prior to the start of study.  
PD-1/L1 treatment progression is defined by meeting all of the following criteria:
    - i. Patients must have had complete response (CR)/partial response (PR) or stable disease (SD) for a duration of at least 6 months prior to progression.
    - ii. Disease progression must have been demonstrated per Response Evaluation Criteria in Solid Tumors (RECIST) version 1.1 (Eisenhauer et al. 2009).
    - iii. The initial evidence of disease progression is to be confirmed by a second assessment no less than 4 weeks from the date of the first documented disease progression, in the absence of rapid clinical progression.
  - c) NSCLC patients with targetable mutations (e.g., ROS1, ALK, BRAF, and EGFR) must have received prior targeted therapy with an approved agent. PD-1/L1 directed treatment is not a requirement for EGFR-mutant patients.

#### **Cohorts D1 and D2: Patients with metastatic CRPC**

- d) Patients must be PD-1/L1 inhibitor therapy naïve;
- e) Patients must have received treatment for metastatic disease; which should have included at least 1 next generation hormonal agent (e.g., Abiraterone, enzalutamide)
- f) Patients with small-cell or neuro-endocrine histologies will be excluded

## Cohort E: Patients with mTNBC

- g) Prior PD-1/L1 inhibitor therapy allowed;
- h) Patients must have received treatment for metastatic disease (at least 1 regimen of cytotoxic chemotherapy for metastatic disease);

Participants are eligible to be included in the study only if **all** of the following criteria apply:

8. Must be able to provide informed consent, as described in Appendix 1, which includes compliance with the requirements and restrictions listed in the informed consent form (ICF) and in this protocol, according to local regulations and are at least 18 years of age.
9. Men with partners of childbearing potential must use a condom during intercourse. Men with partners of childbearing potential or women with childbearing potential must agree to use 2 effective methods of contraception including a highly effective contraceptive method of birth control (Appendix 3) during study treatment and for at least 120 days following the last dose of LY3475070 and pembrolizumab or country requirements, whichever is longer. For patients receiving LY3475070 only, contraception should be maintained for 7 days following the last dose. Additional guidance for contraception during and after study intervention are located in Appendix 3.
10. Women of childbearing potential must have a negative urine pregnancy test at the screening visit followed by a negative serum pregnancy test documented within 24 hours prior to initiation of treatment. If the screening urine test is positive or cannot be confirmed as negative, a serum pregnancy test will be required. Additional guidance for pregnancy testing during and after study intervention is located in Appendix 2 and Appendix 3.
11. Have at least 1 measurable lesion using standard techniques by RECIST version 1.1 (Eisenhauer et al. 2009). **Exception:** patients enrolled in the dose escalation phase and mCRPC patients enrolled in Cohort D1 and D2 are **not** required to have measurable disease.
12. Have a performance status (PS) of 0 or 1 on the Eastern Cooperative Oncology Group (ECOG) scale (Oken et al. 1982).
13. Previous treatments: Have discontinued all previous treatments for cancer and recovered from the acute effects of therapy (except alopecia). Patients must have discontinued from previous treatments, as shown below:

Previous Treatment	Length of Time Prior to First Dose of LY3475070
Endocrine therapies	$\geq 14$ days
Cytotoxic therapies or targeted agents that are small molecule inhibitors	$\geq 21$ days or $\geq 5$ half-lives, whichever is shorter
Biologic agents that are large molecules including immunotherapy (except for patients enrolled in cohorts C1 and C2)	$\geq 28$ days
Limited-field radiotherapy (eg, stereotactic body radiation therapy [SBRT]) with palliative intent	$\geq 14$ days
Other radiotherapy	$\geq 28$ days Participants must have recovered from all radiation-related toxicities, not require corticosteroids, and not have had radiation pneumonitis.
Major surgery, excluding biopsy	Patients with recent major surgery must have recovered, in the opinion of the investigator, from the toxicity and/or complications from the intervention before starting therapy.

14. Have adequate organ function, as defined below:

System	Laboratory Value
Hematologic	
ANC	$\geq 1.5 \times 10^9/L$
Platelets	$\geq 100 \times 10^9/L$
Hemoglobin	$\geq 9$ g/dL

Note: transfusions to increase a patient's hemoglobin level or initiation of erythropoietin or G-CSF therapy to meet enrollment criteria are not allowed in the 14 days preceding the first dose of study drug. If a patient receives transfusions, erythropoietin, or G-CSF therapy <math>\geq 14</math> days prior to the first dose, the hematologic criteria listed above must be met following the 14-day window and prior to the first dose of study therapy.
	
Hepatic	
Total bilirubin	$\leq 1.5 \times ULN$  Isolated bilirubin $> 1.5 \times ULN$ is acceptable if bilirubin is fractionated and direct bilirubin is within normal limits, total serum bilirubin $< 3 \times ULN$ , and Gilbert's Syndrome is confirmed.
ALT and AST	$< 2.5 \times ULN$
Renal	
Calculated creatinine clearance based upon the Cockcroft-Gault formula	$\geq 50$ mL/min/1.73 m 

(see Appendix 6)	
------------------	--

Abbreviations: ALT = alanine aminotransferase; ANC = absolute neutrophil count; AST = aspartate aminotransferase; G-CSF = granulocyte-colony stimulating factor; ULN = upper limit of normal

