## 6.5. Concomitant Therapy

At baseline, record prior and concurrent medications. Record all premedication, supportive care, and concomitant medication continuously at every visit and throughout the study.

The Lilly CRP/CRS should be contacted if there are any questions regarding concomitant or prior therapy. Patients with metastatic CRPC may continue with luteinizing hormone-releasing hormone analogue for testosterone suppression. Zoledronic acid or denosumab given for bone support is allowed to be continued if started 1 week prior to study treatment dosing. However, zoledronic acid or denosumab should not be initiated, especially in metastatic CRPC patients, after study treatment has commenced. No other chemotherapy, immunotherapy, herbal supplements and/or herbal drugs intended to treat cancer, or experimental drugs will be permitted while the patients are in this study.

CCI

If patients can't be switched to alternative therapy Lilly CRP/CRS must be consulted. For a list please consult Appendix 5. Immune-suppressive glucocorticosteroids other than to treat treatment related irAE are also prohibited.

Administration of live vaccines is prohibited during the study and for 3 months following the final dose of study drug. Any medication or vaccine (including over-the-counter or prescription medicines, vitamins, and/or herbal supplements) that the participant is receiving at the time of enrollment or receives during the study must be recorded along with:

- Reason for use
- Dates of administration including start and end dates

Medications or vaccinations specifically prohibited in the exclusion criteria are not allowed during the ongoing trial. If there is a clinical indication for any medication or vaccination specifically prohibited during the trial, discontinuation from trial therapy or vaccination may be required. The investigator should discuss any questions regarding this with the Sponsor. The final decision on any supportive therapy or vaccination rests with the investigator and/or the participant's primary physician. However, the decision to continue the participant on study treatment requires the mutual agreement of the investigator, Lilly CRP/CRS, and the participant.

Listed below are specific restrictions for concomitant therapy or vaccination during the course of the study:

- Antineoplastic systemic chemotherapy or biological therapy
- Immunotherapy not specified in this protocol
- Chemotherapy not specified in this protocol

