### **7.2.1. Discontinuation of Inadvertently Enrolled Patients**

If the sponsor or investigator identify a participant who did not meet enrollment criteria and was inadvertently enrolled, then the patient should be discontinued from study treatment unless there are extenuating circumstances that make it medically necessary for the patient to continue on study treatment. If the investigator and the sponsor CRP agree it is medically appropriate to continue, the investigator must obtain documented approval from the sponsor CRP to allow the inadvertently enrolled participant to continue in the study with or without treatment with investigational product. Safety follow up is as outlined in Section 1.3 (Schedule of Activities), Section 8.3 (Adverse Events and Serious Adverse Events), and Section 8.2 (Safety Assessments) of the protocol.

Please refer to Appendix 7 for discontinuation of inadvertently enrolled patients in the United Kingdom.

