## **10.7. Appendix 7: Country-specific Requirements**

### **10.7.1. Discontinuation of Inadvertently Enrolled Patients in the UK**

If the sponsor or investigator identifies a participant who did not meet enrollment criteria and was inadvertently enrolled, then the participant should be discontinued from study treatment and safety follow up should be performed as outlined in Section 1.3 (Schedule of Activities), Section 8.3 (Adverse Events and Serious Adverse Events), and Section 8.2 (Safety Assessments) of the protocol.

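### The 14-day endocrine washout in inclusion criterion 13 has no exception for the LHRH analogue that Section 6.5 lets mCRPC patients keep taking

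*Protocol*

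**What the plan says.** Criterion 13 in Protocol Section 5.1 belongs to the block of criteria that all participants must meet, whatever their cohort. It requires patients to "Have discontinued all previous treatments for cancer and recovered from the acute effects of therapy (except alopecia"). A table then gives the minimum gap between each class of prior treatment and the first dose of LY3475070. The row headed "Endocrine therapies" asks for at least 14 days and carries no exception. Another row of the same table does carry one: "Biologic agents that are large molecules including immunotherapy (except for patients enrolled in cohorts C1 and C2").

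Section 6.5 on concomitant therapy says: "Patients with metastatic CRPC may continue with luteinizing hormone-releasing hormone analogue for testosterone suppression". It also says: "The Lilly CRP/CRS should be contacted if there are any questions regarding concomitant or prior therapy".

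Section 5 opens by stating that prospective approval of deviations from the enrollment criteria, "also known as protocol waivers or exemptions, is not permitted". Section 8 repeats that waivers are not allowed.

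**The concern.** A patient who continues an LHRH analogue through study entry has not stopped it 14 days earlier. The two rules therefore cannot both be met by a patient who uses the permission in Section 6.5.

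Eligibility is judged against Section 5.1, and the permission is not there. A site that reads criterion 13 literally either turns the patient away or stops testosterone suppression before baseline. A site that follows Section 6.5 enrolls a patient who does not meet an enrollment criterion as written.

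The second route raises a question the protocol leaves open. For an inadvertently enrolled patient who did not meet enrollment criteria, Section 7.2.1 says "then the patient should be discontinued from study treatment unless there are extenuating circumstances that make it medically necessary" to continue, and the sponsor's physician must document approval. The UK version in Appendix 7 has no such exception: "then the participant should be discontinued from study treatment and safety follow up should be performed as outlined in Section 1.3". Neither section says whether a patient enrolled under Section 6.5 counts as inadvertently enrolled. SAP Section 6.11 also summarizes significant violations by category, including inclusion and exclusion criteria, with some identified programmatically. A literal check of criterion 13 could flag these patients.

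If some sites stop suppression and others do not, PSA, bone and RECIST readouts in mCRPC could become noisier. PSA matters most, because Section 8.1.3 uses PSA change to judge response and progression in mCRPC patients without measurable disease.

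**Working it through.** The main check compares text; only the size needs arithmetic.

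**Comparing the rules**

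| Point | Section 5.1, criterion 13 | Section 6.5 |
|---|---|---|
| Who | Every participant | mCRPC patients |
| What | All previous cancer treatments; endocrine therapies as a class | LHRH analogue for testosterone suppression |
| Requirement | Stopped at least 14 days before first LY3475070 dose | May be continued |
| Cross-reference to the other rule | None | None |

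1. *Does criterion 13 reach mCRPC patients?* Yes. It applies to everyone, so it covers Cohorts D1 and D2 and any mCRPC patients in Cohorts A and B.
2. *Is an LHRH analogue an endocrine therapy?* The protocol does not define the term. A hormone analogue given to suppress testosterone in prostate cancer fits its plain meaning. This is an assumption.
3. *Is there an exception elsewhere?* The prostate criteria (3f for Phase 1a, 7d to 7f for Cohort D) contain none, and they do not point to Section 6.5.
4. *Can the silence be read as an exception?* Section 5.1 writes its exceptions out. The biologics row exempts C1 and C2, and criterion 11 exempts dose-escalation patients and mCRPC patients in D1 and D2 from needing measurable disease. Against that pattern, an endocrine row with no exception reads as having none.
5. *Can it be settled patient by patient?* A question to the sponsor's physician can clarify intent. It cannot waive an enrollment criterion.

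**Size**

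Inputs: Protocol Section 9.5 places the Cohort D interim after 10 monotherapy patients, with about 20 on combination, and allows 20 more on combination. The synopsis caps Cohort D at 50.

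- Ceiling at the interim: 10 + 20 = about 30.
- Ceiling after expansion: 30 + 20 = 50, which agrees with the stated cap.
- The documents do not give the share of mCRPC patients on an LHRH analogue. Taking 0% to 100%, the range is 0 to about 30 before expansion and 0 to 50 after it.
- The number of mCRPC patients in Cohorts A and B is not stated, so no figure is attached to them.

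**The case against.** The best defense is that Section 6.5 already answers the question. It names this population, this drug class and its purpose, and a specific permission ordinarily governs a general washout. Criterion 13 is labeled as dealing with previous treatments, and ongoing background suppression may not be one. The 14-day row would still have work to do, because criteria 3f and 7e require a prior next-generation hormonal agent such as abiraterone or enzalutamide. The list of on-study restrictions in Section 6.5 does not name endocrine therapy. The literal reading also makes little sense in a population defined as castrate resistant, and it would leave the permission to continue with nothing to apply to. On consequences, a patient knowingly enrolled under an express permission does not sit naturally under a rule for inadvertent enrollment, and no harm has been quantified.

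Much of this stands. The intent is recoverable, most sites will probably act on it, and the discontinuation and readout consequences are possibilities only. In Cohort D any readout effect would not be systematically tied to arm, because patients are randomized.

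The argument from the word previous is strained. A rule requiring a drug to be stopped a set time before dosing is aimed at drugs that might otherwise still be running. Showing what the sponsor probably meant does not make the two rules consistent, and the no-waiver statement is a reason to correct the criterion itself.

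**Conclusion.** The concern holds. For mCRPC patients on an LHRH analogue, criterion 13 and Section 6.5 contradict each other as worded, and nothing in the protocol reconciles them. Followed literally, the eligibility rule excludes such patients or requires suppression to be stopped.

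The reach is bounded by the Cohort D ceilings above, plus the uncounted mCRPC patients in Cohorts A and B. Those figures count patients who could meet the conflicting wording; they do not predict screen failures, treatment discontinuations or biased readouts. The conclusion assumes that an LHRH analogue given for testosterone suppression is an endocrine therapy and a cancer treatment in the sense of criterion 13.

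No sample size, interval or analysis in the SAP changes. This should be corrected because an eligibility rule that is wrong as written for a named population can be put right with one clause.

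**What to change.** Add to the endocrine row of the criterion 13 table: *except LHRH analogues for testosterone suppression in mCRPC patients, which may be continued (see Section 6.5)*. Because the general sentence above the table also demands that all previous cancer treatments be stopped, the clause should be understood to qualify that sentence too. The 14-day washout then applies only to other endocrine agents, including the next-generation hormonal agents named in criteria 3f and 7e.

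The cost is one clause in the eligibility table, with no extra patients, visits, tests or data fields. Concomitant medications from 28 days before the first dose are already recorded under Section 6.5, so LHRH analogue use at entry can be described from data the trial collects anyway.
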